6 STATISTICAL CONSIDERATIONS

6.1 Descriptive Statistics

Unless otherwise specified, continuous data will be summarized descriptively using the number in the analysis set (N), the number of observations (n), mean, standard deviation (SD), median, minimum and maximum. Categorical data will be summarized using frequency counts and percentages. The denominator for the percentages will be the total number of subjects in the treatment group and analysis population being presented, unless otherwise specified.

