1.6 Background of the Adjuvant AS03

The adjuvant AS03 is an established effective adjuvant used in the formulations for Arepanrix™ and Pandemrix™ and is manufactured by GlaxoSmithKline. The AS03-adjuvanted pandemic influenza vaccines have been shown to be more immunogenic than non-adjuvanted vaccines, offering the potential of cross-clade immunity and feasibility of antigen-sparing. High efficacy and effectiveness have been demonstrated for AS03-adjuvanted H1N1 pandemic influenza vaccines in a wide range of populations [Garcon 2012]. Clinical data with AS03-adjuvanted antigen-sparing formulations have shown that immunization against influenza caused by the potential pandemic subtypes H5N1, H1N1, H7N1, H7N9, and H9N2 has demonstrated satisfactory immunogenic potency, as measured by haemagglutinin-inhibition titers, with reduced antigen doses in adults [Baz 2013, Jackson 2015, Lansbury 2017, Leroux-Roels 2007, Madan 2017, Madan 2017a, Madan 2017b, McElhaney 2013, Yang 2013, Yin 2011]. Also, AS03-adjuvanted H5N1 vaccines were shown to induce cross-clade neutralizing antibody responses [Leroux-Roels 2007] and antibody affinity maturation [Khurana 2018].

Data from clinical trials with over 55 000 vaccinated subjects showed that AS03-adjuvanted influenza vaccines exhibited an acceptable safety profile [Cohet 2019, Garcon 2012, Vaughn 2014]. Increased reactogenicity, both local and general, is consistently noted for AS03-adjuvanted vaccines compared with the corresponding unadjuvanted vaccines [Garcon 2012, Launay 2013, Nolan 2014, Waddington 2010]. Most symptoms were mild to moderate in intensity and of short duration. An increased risk of narcolepsy was observed in some individuals after the vaccination campaign with Pandemrix™ in 2009-2010. A similar risk of narcolepsy was not identified with other non-adjuvanted influenza vaccines or other AS03-adjuvanted vaccines, like Arepanrix™ [Montplaisir 2014, Cohet 2015]. Current data suggest that cases of narcolepsy seen immediately following the 2009-2010 pandemic were most likely the result of an immune cascade, triggered by CD4 T cell cross-reactivity to HA proteins from the H1N1 virus itself and hypocretin.

Research is continuing to assess whether either of the main components of the 2009/2010 flu pandemic vaccine (e.g., the viral proteins in the form used in the vaccine or the AS03 adjuvant)

may have contributed to the reaction.

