12.1.9 Causal Relationship

The Investigator must make the determination of relationship to the study vaccine for each unsolicited AE. The causal relationship of all solicited local and systemic AEs will be considered related. The Investigator should decide whether, in his/her medical judgment, there is a reasonable possibility that the event may have been caused by the investigational vaccine. If there is any valid reason, even if undetermined or untested, for suspecting a possible cause-and-effect relationship between the investigational vaccine and the occurrence of the AE, then the AE should be considered “definitely related”, “probably related”, or “possibly related”. Otherwise, if no valid reason exists for suggesting a possible relationship, then the AE should be classified as “probably not related” or “definitely not related”. The following guidance should be followed:

Definitely Not Related:	The AE is clearly not related to the administration of the study vaccine. Another cause of the event is most plausible; and/or a clinically plausible temporal sequence is inconsistent with the onset of the event and the study vaccine administration; and/or a causal relationship is considered biologically implausible.
Probably Not Related:	There is no medical evidence to suggest that the AE is related to the study vaccine. The event can be readily explained by the subject's underlying medical condition or concomitant therapy or lacks a plausible temporal relationship to the study vaccine.
Possibly Related:	A direct cause and effect relationship between the study vaccine and the AE has not been demonstrated but there is a reasonable possibility that the event was caused by the study vaccine.
Probably Related:	There probably is a direct cause and effect relationship between the AE and the study vaccine. A plausible biologic mechanism and temporal relationship exist and there is no more likely explanation.
Definitely Related:	There is a direct cause and effect relationship between the AE and the study vaccine.

AE outcomes will be classified as recovered/resolved, not recovered/not resolved, recovered/resolved with sequelae, recovering/resolving, or death.

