13.3 Contraindications for Subsequent Vaccination

The following events constitute absolute contraindication to the further administration of the study treatments at Day 21; if any of these events occur during the study, the subject will not receive an additional dose of vaccine but will continue with the Day 128 scheduled visit (see Section 9.3.12), the Day 201 scheduled visit (see Section 9.3.13), the Day 386 scheduled visit (see Section 9.3.14) and all telephone contact visits at the discretion of the Investigator:

- ♦ Pregnancy (see Section 11.1.7);
- ♦ Clinically-apparent hypersensitivity of any grade that is considered by the site Investigator to be related to the investigational product in response to first vaccine administration;
- ♦ Have a laboratory-confirmed SARS-CoV-2 infection;
- ♦ Acute disease within 48 hours prior to vaccination (acute disease is defined as presence of any moderate or severe acute illness with or without a fever);
- ♦ Diagnosis of pIMD;
- ♦ Experience a possibly related, probably related, or definitely related SAE or Grade 3 or higher related AE that cannot be clearly attributed to another cause;
- ♦ Discovery of any health condition which, in the Investigator’s opinion, may place the subject at increased risk from receipt of further vaccination; or discovery of a change in the subject’s status which may render him/her unable to comply with protocol-mandated safety

follow-up. If an AE occurred prior to or at the time of the Day 21 scheduled visit, the subject may be discontinued at the discretion of the Investigator or the subject may be vaccinated at a later date, however, within the time window specified in the protocol (see Section 9.3.6.1). The subject must be followed until resolution of the event as with any AE (see Section 12.1.2).

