5 ANALYSIS SET

The statistical analysis will be based on separate analysis sets, defined as follows:

Safety Analysis Set (SAS): All subjects who received at least one dose of either the MT-2766 or placebo.

Immunogenicity Intent-to-treat (ITT) Set All subjects who receive at least one dose of either the MT-2766 or placebo and who have at least 1 post-baseline Immunogenicity assessment.

Immunogenicity Per Protocol (PP) Set Immunogenicity ITT set who do not have any major protocol violations, and who received either the MT-2766 or placebo. For the Day 21 analysis, this should include the subjects who received the first vaccine dose and had Day 0 and Day 21 immunogenicity sample collections. For the Day 42 analysis, this should include the subjects who received both vaccine doses and had Day 0 and Day 42 immunogenicity sample collections. For the Day 128 analysis, this should include the subjects who received both vaccine doses and had Day 0 and Day 128 immunogenicity sample collections. For the Day 201 analysis, this should include the subjects who received both vaccine doses and had Day 0 and Day 201 immunogenicity sample collections.

All safety analyses will be performed using the SAS. The analyses of all immunogenicity endpoints will be performed using the Immunogenicity PP set as the primary analysis population, and the immunogenicity ITT set, as a secondary analysis population.

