7.3 Data Handling Convention for Missing Data

Concomitant medication:

There is no imputation for completely missing dates.

Missing or partial concomitant medication start date:

- If only DAY is missing, use the first day of the month.
- If DAY and Month are both missing, use the first day of the year.

Missing or partial concomitant medication stop date:

- If only DAY is missing, use the last day of the month.
- If DAY and Month are both missing, use the last day of the year.
- If DAY, Month and year are all missing, assign ‘continuing’ status to stop date.

Immunogenicity:

Missing immunogenicity data will be retained as missing.

Adverse events:

There is no imputation for completely missing dates.

Missing or partial AE date:

No imputation of AE partial/missing start/end dates or times will be performed. In case of missing or incomplete AE onset date/time, the AE will be included in the analysis unless the incomplete AE onset date/time information unequivocally indicates that the AE started prior to Day 0.

If an AE allocation to a reporting cannot be unequivocally ascertained due to partial/missing date, the AE will be allocated to all relevant periods.

Missing relatedness and intensity of AEs will not be imputed and will be presented as “Missing”.

Other safety:

For safety summaries, only observed data will be used. Unless otherwise specified, missing safety data will not be imputed.

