8.3 Safety Assessments

All safety data will be listed.

Safety assessments will be made on the SAS.

Adverse events analyses will be presented for the following reporting period, as applicable:

- Day 0-21 period after vaccination 1: Any AEs meeting the following criteria will be allocated to the first vaccination (vaccination 1) and included in the Day 0-21 analysis for first vaccination:
 - Any AEs with:
 - onset date/time < date and time of second vaccine administration, if second vaccination is done,
 - else if vaccination 2 not performed, any AEs with onset date \leq date of vaccination 1 + 21
- Day 0-21 period after vaccination 2: Any AEs meeting the following criteria will be allocated to second vaccination (vaccination 2) and included in the Day 0-21 analysis for second vaccination:
 - Any AEs with onset date/time \geq Date/time of vaccination 2 and with onset date \leq date of vaccination 2 + 21.

- Day 0-21 period after last vaccination: Any AEs meeting the following criteria will be included in the Day 0-21 period after last vaccination:
 - Any AEs with onset date \leq date of last vaccination + 21 i.e.:
 - Any AEs with onset date \leq date of vaccination 2 + 21, if vaccination 2 is performed
 - Any AEs with onset date \leq date of vaccination 1 + 21, if vaccination 2 is not performed.

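### The stated denominator for safety percentages after vaccination 2 includes subjects who never received it, so those rates are understated whenever dose 2 is missed

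*SAP*

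**What the plan says.** **Denominator.** The general rule is in SAP 6.1: "The denominator for the percentages will be the total number of subjects in the treatment group and analysis population being presented, unless otherwise specified". SAP 5 defines the Safety Analysis Set as everyone given at least one dose and states: "All safety analyses will be performed using the SAS". SAP 8.3 names the same population again.

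SAP 8.3 then defines its reporting periods. The entry for the second dose opens "Day 0-21 period after vaccination 2: Any AEs meeting the following criteria will be allocated to second vaccination (vaccination 2" and goes on to the onset limits. Another entry reads "Day 0-21 period after last vaccination: Any AEs meeting the following criteria will be included in the Day 0-21 period after last vaccination", with separate onset limits according to whether vaccination 2 was given. These rules decide which events count. Neither they nor SAP 8.3.1 to 8.3.2.2 say who is in the denominator.

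A missed second dose is foreseen, both in SAP 8.3 and in protocol 13.3 and 13.5. Under the protocol, such a subject may stay in follow-up.

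**Day 43-201.** SAP 2.2.2 lists SAEs, MAAEs, AEs leading to withdrawal, AESIs and deaths in this window as a secondary endpoint, and protocol 14.4.3 plans the summary by treatment. SAP 8.3 defines three periods: after vaccination 1, after vaccination 2 and after last vaccination. SAP 8.3.2 adds a cumulative summary up to end of study (EOS). SAP 10 reports that Group 3 was not enrolled and that Day 386 and some other items were not measured. It does not mention this analysis.

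**The concern.** The primary safety endpoint concerns reactions in a set time after each injection. Someone who did not get the second injection is not at risk of a reaction to it. Read together, SAP 6.1, 5 and 8.3 nevertheless keep that person in the denominator, so following the SAP literally lowers every percentage in the after-vaccination-2 tables. The SAP handles the same problem differently for immunogenicity: from Day 42 on, the Per Protocol set requires both doses. At stake is how common reactions to the second dose appear to be in the trial's main safety tables.

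The secondary point is a gap in implementation. A declared endpoint has no onset window and no denominator in the document that specifies the tables.

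**Working it through.** The documents state no figure to reproduce here. The sample size does not rest on a power calculation, and no post-dose-2 event rate or missed-dose count is given.

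**Inputs.** Group sizes come from SAP 3.2: 125 subjects at 4:1, so 125 × 4/5 = 100 and 125 × 1/5 = 25. I assume that all 125 received dose 1. Event rates and the numbers missing dose 2 (m) are also assumptions.

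**1. Understatement within an arm.** Let x be the subjects with an event after dose 2 and N the Safety Analysis Set.
- Rate under the SAP rule: x/N
- Rate among dose-2 recipients: x/(N − m)
- Ratio of the first to the second: (N − m)/N = 1 − m/N

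Each missed subject therefore costs 1/100 = 1% relative in Group 1 and 1/25 = 4% relative in Group 2.

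| Arm | m | Among recipients | Under the SAP rule |
|---|---|---|---|
| Group 1 | 0 | 40/100 = 40.0% | 40/100 = 40.0% |
| Group 1 | 5 | 38/95 = 40.0% | 38/100 = 38.0% |
| Group 1 | 10 | 36/90 = 40.0% | 36/100 = 36.0% |
| Group 1 | 20 | 32/80 = 40.0% | 32/100 = 32.0% |
| Group 2 | 0 | 5/25 = 20.0% | 5/25 = 20.0% |
| Group 2 | 1 | 5/24 = 20.8% | 5/25 = 20.0% |
| Group 2 | 5 | 4/20 = 20.0% | 4/25 = 16.0% |

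**2. Difference between arms.** Take 40.0% and 20.0% among recipients, a difference of 20.0 points.
- 5 of 100 and 0 of 25 miss dose 2: 38.0 − 20.0 = 18.0 points, too small.
- 5 of 100 and 5 of 25 miss dose 2: 38.0 − 16.0 = 22.0 points, too large.

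The direction depends on the missed-dose counts in both arms, which the documents do not give.

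**3. Periods for which all dosed subjects are right.** Everyone in the Safety Analysis Set is at risk after vaccination 1. The after-last-vaccination period has its own rule for subjects without dose 2. The up-to-EOS summary is cumulative from the first dose. None of these needs changing.

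**4. Day 43-201 cannot be recovered by subtraction.** Suppose 12 subjects have an event by Day 42, 10 have one in Day 43-201, and 4 are in both groups. The cumulative table shows 12 + 10 − 4 = 18. Subtracting gives 18 − 12 = 6, not 10.

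**5. Where a late period must start.** Dose 2 may fall on Day 19 to 23 (Day 21 ± 2), so the 21-day period after it ends between Day 19 + 21 = 40 and Day 23 + 21 = 44. A fixed start on Day 43 then leaves Days 41-42 uncovered in the first case and counts Days 43-44 twice in the second. Without dose 2 the period ends on Day 21, and Days 22-42 are uncovered.

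**The case against.** **The rule is only a default.** SAP 6.1 allows exceptions, and table shells, which are not in these documents, may already set a per-dose N. SAP 7.3 also says "For safety summaries, only observed data will be used", which could be read as leaving out subjects with nothing observed after dose 2. The possibility of shells stands and limits confidence. The SAP 7.3 sentence does not help much: it belongs to the missing-data rules and names no denominator.

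**All dosed subjects is a legitimate descriptive denominator.** It keeps the groups as randomised, whereas recipients are selected partly on how they tolerated dose 1. That selection is real, and it is why missed doses need to be shown. But the endpoint is tied to the second injection, and a percentage that includes people who did not have it answers another question.

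**The size is assumed.** This is correct. It is nil if everyone received dose 2.

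**A stronger reading that a reader might infer** is that the rule flatters the vaccine against placebo. Protocol 13.3 withholds dose 2 after a related "SAE or Grade 3 or higher related AE that cannot be clearly attributed to another cause". Protocol 12.1.9 says "The causal relationship of all solicited local and systemic AEs will be considered related", and protocol 1.6 says "Increased reactogenicity, both local and general, is consistently noted for AS03-adjuvanted vaccines compared with the corresponding unadjuvanted vaccines". The documents do not carry the inference that far. The last statement compares adjuvanted with unadjuvanted influenza vaccines, not with placebo, and the same section calls most symptoms mild to moderate, whereas the AE part of that contraindication needs Grade 3 or higher. Other reasons in protocol 13.3, such as SARS-CoV-2 infection, acute illness and pregnancy, can fall on either arm. So can withdrawal under protocol 7.8 after a request for public vaccination.

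**On Day 43-201,** protocol 14.4.3 still prescribes the summary, SAP 1 overrides the protocol only for details that the SAP describes, and the up-to-EOS summary counts the events. This stands and makes the point a smaller one.

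**Conclusion.** The denominator point holds on the supplied text. Post-dose-2 safety percentages are understated by the factor n(dose 2)/n(Safety Analysis Set). The conclusion assumes that no unseen table shell sets a per-dose N, and the 1% and 4% figures assume that the planned 100 and 25 subjects were dosed. No systematic bias in the vaccine-placebo difference can be claimed in either direction. The correction is worth making because the affected rates belong to the primary safety endpoint and the SAP itself expects some second doses to be missed.

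The Day 43-201 gap is secondary. A reader might infer that the endpoint was abandoned. The documents do not say so: it remains declared and planned, but without an onset window or denominator in SAP 8.3.

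**What to change.** **Denominator (SAP 8.3).** State that percentages in the after-vaccination-2 tables (solicited, immediate and unsolicited AEs) use Safety Analysis Set subjects who received dose 2. Show the number missing dose 2, and the reasons, by arm. Keep all Safety Analysis Set subjects for the after-vaccination-1, after-last-vaccination and up-to-EOS tables.

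**Day 43-201.** Either list the omission in SAP 10 or add the period to SAP 8.3, by treatment:
- Start it the day after the after-last-vaccination period ends: vaccination 2 + 22, or vaccination 1 + 22 if dose 2 was not given. In the latter subjects, identify events before Day 43.
- State the end day. SAP 7.2 centres the Day 201 visit on vaccination 2 + 180 with a window of 14 days, so the visit can fall as late as vaccination 2 + 194.
- Use subjects still in follow-up at the start as the denominator, and show follow-up time by arm.

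SAP 10 should also say what happens to the Day 202-386 period, which SAP 2.2.2 still declares.

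**Cost.** SAP wording and table programming only, with no new data. There is one extra set of tables, and the post-dose-2 rate will describe dose-2 recipients only.

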6.2 Statistical Tests

Unless otherwise specified, all formal statistical tests will be done at two-sided significance level of 0.05. Point estimates will be accompanied with two-sided 95% CIs where applicable.

7 DATA CONVENTIONS

7.1 Analysis Variable Definitions

7.1.1 Study Subjects

7.1.1.1 Demographic and Other Baseline Characteristics

BMI will be recalculated to 1 decimal place using the following formula:

$$\text{BMI (kg/m}^2\text{)} = \text{weight at screening (kg)} / \{\text{height at screening (m)}\}^2$$

Significant comorbidities will be defined as co-morbid conditions that puts them at higher risk for severe COVID-19 disease. These significant comorbidities include obesity, hypertension, type 1 or type 2 diabetes, chronic obstructive pulmonary disease (COPD), cardiovascular diseases, chronic kidney diseases, or be immunocompromised persons (e.g., treatment-controlled HIV infection, organ transplant recipients, or patients receiving cancer chemotherapy).

7.1.1.2 Medical History

Medical history will be coded according to the MedDRA version 24.1.

7.1.1.3 Prior or Concomitant Medication

Medications will be coded according to the WHO Drug Dictionary (WHO-DD) Global B3 version Sep 2021.

(1) Prior Medication

Prior medication is any medication that was started prior to study vaccine date and ended before study vaccine date.

(2) Concomitant Medication

Concomitant medication is a medication that starts on or after vaccination date/time at Day 0 or starts before vaccination and is still on-going at the time of the study vaccine.

7.1.2 Immunogenicity assessments

7.1.2.1 Geometric Mean Titer (GMT)

Continuous immunogenicity endpoints will be logarithmically transformed with 10 as base for analysis. GMT point estimates and the corresponding two-sided 95% CI by treatment group will be calculated as the antilog of the mean and 95% CI of log transformed titer values.

7.1.2.2 Geometric Mean Fold Rise (GMFR)

GMFR will be defined as the geometric mean of the ratio of GMTs (Day 21/Day 0, Day 42/Day 0, Day 128/Day 0, Day 201/Day 0).

7.1.2.3 Seroconversion (SC) Rate

SC rate is defined as the proportion of subjects achieving SC in the analysis set i.e. subjects with:

- For subjects with detectable Nab/IgG titer at Day 0 (i.e. baseline Nab/IgG titer ≥ 10): a ≥ 4 -fold increase in Nab/IgG titers between Day 0 and Day 21/42/128/201, respectively.
- For subjects with undetectable Nab/IgG titer at Day 0 (i.e. baseline Nab/IgG titer < 10): Nab/IgG titer of ≥ 40 on Day 21/42/128/201, respectively.

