7.1.2.4 Immunogenicity values

If antibody titers and concentrations are below the cutoff, i.e the result is of the form ‘<xx’, the value will be set to $0.5 * xx$ before performing GMT calculations. Only samples for which PBMC preparation was performed within 8 hours will be used for analysis.

“Below LOD” in IFN- γ and IL-4 data should be considered as “0”.

“NR” in IFN- γ and IL-4 data should be considered as “not reportable” results.

Value of “< 100” and “IR” in Nab data due to hemolyzed samples should be considered as “not reportable” results.

“>ULOQ” in Nab data are results above ULOQ at the maximal dilution and the “>ULOQ” value should be assigned as “64000”.

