10 CHANGE FROM THE PROTOCOL

Group 3 was not enrolled. Also, because the study was discontinued, the items on Day 386 and some items were not measured. Only the collected data were included in the tabulation and listings.

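### The seroconversion denominator in the SAP takes in subjects who have no titre at the visit, which conflicts with its available-data rules and dilutes the secondary ITT rate

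*SAP*

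**What the plan says.** **Definition.** SAP 7.1.2.3, for both Nab and IgG: "SC rate is defined as the proportion of subjects achieving SC in the analysis set i.e. subjects with" a fourfold rise from a detectable Day 0 titre, or a titre of at least 40 from an undetectable one. Protocol 14.4.2 also takes the proportion over the analysis set.

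**Default denominator.** SAP 6.1: "The denominator for the percentages will be the total number of subjects in the treatment group and analysis population being presented, unless otherwise specified". The sections that analyse SC (SAP 8.2.1.1, 8.2.2.1 and 8.2.2.4) give no other denominator. They ask for Fisher's exact test and Clopper-Pearson 95% intervals.

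**Analysis sets.** SAP 5 admits to the immunogenicity ITT set subjects with at least one dose "who have at least 1 post-baseline Immunogenicity assessment". The visit does not matter. The PP set is defined visit by visit, for example: "For the Day 201 analysis, this should include the subjects who received both vaccine doses and had Day 0 and Day 201 immunogenicity sample collections". The SAP takes "the Immunogenicity PP set as the primary analysis population, and the immunogenicity ITT set, as a secondary analysis population".

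**Missing and unusable results.** SAP 7.3: "Missing immunogenicity data will be retained as missing". Under SAP 7.1.2.4, certain Nab values from haemolysed samples "should be considered as “not reportable” results". SAP 10 records that "because the study was discontinued, the items on Day 386 and some items were not measured", and adds that tabulations and listings contain only data actually collected.

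**The concern.** SC status needs two titres, one at Day 0 and one at the visit. A subject whose only post-baseline sample is from Day 21 belongs to the ITT set for good. At Days 42, 128 and 201 that subject cannot be shown to have seroconverted, yet under SAP 7.1.2.3 and 6.1 is still counted below the line. The rate then mixes retention with antibody response. The geometric mean titre (GMT) and fold rise (GMFR) from the same visit can use only the titres that exist, so adjacent persistence results would describe different subjects.

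Late missingness is plausible. After the Day 42 key open, public vaccination is recommended to placebo subjects (protocol 5.5; SAP 3.2 says allowed), and those who take it are withdrawn. Group 1 may follow if efficacy is judged inadequate or unconfirmable. The study was also discontinued. SC rate is a primary parameter at Days 21 and 42 and a secondary one later, so two programmers reading the same SAP should not be able to produce different tables.

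**Working it through.** **No figure to reproduce.** The documents give no SC rate, dropout rate or power calculation. The planned sizes are 100 in Group 1 and 25 in placebo (SAP 3.2). All counts with titres and all SC counts below are assumptions.

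**Formula.** Let s be the SC rate among subjects with both titres and d the fraction of the set lacking one. The whole-set rate is s × (1 − d); the rate among evaluable subjects is s.

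**ITT set, Group 1, assumed size 98** (Clopper-Pearson 95% intervals):

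| Assumed visit and counts | Whole-set denominator | Evaluable denominator |
|---|---|---|
| Day 42: 93 with titres, 91 SC | 91/98 = 92.9% (85.8–97.1) | 91/93 = 97.8% (92.4–99.7) |
| Day 201: 70 with titres, 66 SC | 66/98 = 67.3% (57.1–76.5) | 66/70 = 94.3% (86.0–98.4) |
| Day 201: 40 with titres, 38 SC | 38/98 = 38.8% (29.1–49.2) | 38/40 = 95.0% (83.1–99.4) |

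Check on the second row: s = 66/70 = 0.943 and d = 28/98 = 0.286, so s(1 − d) = 0.943 × 0.714 = 0.673. The third row needs d = 58/98 = 59%, an extreme case.

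**Range.** With 100 in the set and s = 95%, the whole-set rate is 90%, 86%, 76%, 66% and 48% for 5%, 10%, 20%, 30% and 50% missing (counts rounded to whole subjects). With s = 80% it is 76%, 72%, 64%, 56% and 40%; with s = 60% it is 57%, 54%, 48%, 42% and 30%.

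**Placebo.** If nobody seroconverts, the point estimate is 0 either way, but the interval is too narrow: 0–13.7% on 25, against 0–21.8% on 15 evaluable or 0–52.2% on 5.

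**Fisher's test.** Against an assumed 0/25, the whole-set comparison gives p < 0.001 throughout that range; the weakest case is 30/100 against 0/25, p = 0.0005. The evaluable version of that case with only 5 placebo subjects left, 30/50 against 0/5, gives p = C(25,5)/C(55,5) = 53,130/3,478,761 = 0.015. Both are below the two-sided 0.05 level of SAP 6.2.

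**PP set.** Dropouts leave it at each visit, and SAP 7.2 also removes samples taken outside the window. Membership turns on a sample being collected, not on a usable result. With 100 collected and 3 not reportable, 92/100 = 92.0% against 92/97 = 94.8%; with 10 not reportable, 86/100 = 86.0% against 86/90 = 95.6%.

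**The case against.** The best defence is that the SAP already intends an available-data analysis. SAP 7.3 leaves missing titres missing, so SC status derived from them is naturally missing too, and SAP 10 confines the tabulations to collected data. The default in SAP 6.1 yields where something else is specified, and these two sections might be taken to do that. The primary population is visit-specific, so dropouts never dilute it. The study has no power calculation, and protocol 11.2.1 plans descriptive comparison of the groups.

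Much of this stands. A reader might infer that the SAP has a rule counting missing titres as failures. It has none; that outcome is only a consequence of the denominator wording. Nor would the rate track dropout in place of antibody loss: it would fall with both, and the two could not be separated. A reader might also expect the Fisher comparison to be overturned. That is unlikely, because the only withdrawal route that opens unconditionally at key open is in placebo, where SC is assumed near zero.

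What does not stand is that SAP 7.3 or SAP 10 settles the matter. One bars imputation and the other describes what is tabulated; neither says what the SC count is divided by. SAP 7.1.2.3 and 6.1 do, and they give the whole set.

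**Conclusion.** The point holds as a conflict between sections that must be reconciled. Followed literally, the stated denominator gives a diluted rate and a wrong interval in the secondary ITT set: the rate among evaluable subjects is multiplied by the fraction who have titres. On the assumed counts that is about 5 percentage points at Day 42 (97.8 − 92.9) and 27 at Day 201 (94.3 − 67.3). The real size depends on Group 1 missingness, which the documents make plausible but do not quantify.

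The primary PP analysis is affected only by collected Nab samples with no reportable result, whose frequency is not given. The harm is to estimates and intervals, not to the likely conclusion of the between-group test. It should be corrected because the SC rate will be read as a measure of antibody response and the correction is cheap.

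**What to change.** In SAP 7.1.2.3, state that the SC rate at each visit, for Nab and for IgG, is the number of subjects achieving SC divided by the number in the analysis set with a reportable Day 0 titre and a reportable titre at that visit. Say that this replaces the SAP 6.1 default. Use the same denominator for the percentage, the Clopper-Pearson interval and Fisher's test, in both the ITT and PP sets, and print n/N beside each rate. If a missing-as-failure version is wanted, label it as a sensitivity analysis.

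The cost is one sentence and a denominator change in the SC tables; no new data are needed. The small downside is that the ITT denominator will vary by visit, as it already does for GMT.
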